Physician-directed standard background therapies will include dual oral antiplatelet therapy with aspirin and an approved oral P2Y₁₂ antagonist as well as antithrombotic therapy with unfractionated heparin. Physician-directed P2Y₁₂ antagonist therapy and choice of femoral or radial access site must be pre-specified prior to randomization.

The first 159 patients were randomized to the following two treatment arms on a 1:1 basis:

1. Tirofiban (25 µg/kg bolus followed by a 0.15 µg/kg/min infusion for the duration of the PCI procedure plus a minimum of one hour and up to a maximum of two hours post-PCI).
2. Eptifibatide (180 µg/kg bolus followed by a 2.0 µg/kg/min infusion for 18 hours post-PCI [minimum 12 hours mandated], with a second 180 µg/kg bolus 10 min after the first).

The three treatment arms for enrollment after the 159th patient were:

1. Short Tirofiban (25 µg/kg bolus followed by a 0.15 µg/kg/min infusion for the duration of the PCI procedure plus a minimum of one hour and up to a maximum of two hours post-PCI).
2. Eptifibatide (180 µg/kg bolus followed by a 2.0 µg/kg/min infusion for 18 hours post-PCI [minimum 12 hours mandated], with a second 180 µg/kg bolus 10 min after the first).
3. Long Tirofiban (25 µg/kg bolus followed by a 0.15 µg/kg/min infusion for 18 hours post-PCI) [minimum 12 hours mandated].

Enrolment in the Long Tirofiban arm has been completed. Enrolment continues in the Short Tirofiban and Eptifibatide arms as outlined above.

SAMPLE SIZE: Approximately 550 patients will be enrolled in the trial. The rate of the primary composite endpoint is assumed to be 51% in both the eptifibatide and tirofiban treatment groups. The absolute margin for the difference between the eptifibatide and the short tirofiban group is set at 19.1%. A sample size of approximately 500 for the comparison between the short tirofiban and the eptifibatide group was obtained by setting a power at 99% and a 1-sided alpha at 0.025. For the second test, a sample size of approximately 350 for the comparison between the short tirofiban and the long tirofiban group was obtained by setting power at 94.5% and a 1-sided alpha at 0.025. For the third test, a sample size of approximately 350 for the comparison between the long tirofiban and the eptifibatide group was obtained by setting power at 94.5% and a 1-sided alpha at 0.025.

DOSAGE/DOSAGE FORM, ROUTE, AND DOSE REGIMEN

Aspirin:	As per local practice and physician discretion

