2.6 Sample Size

The primary outcome variable for this trial is the composite of death, PPM, uTVR or REPLACE-2 major bleeding.

Sample size calculations ensure that the one-sided non-inferiority hypothesis of the first primary outcome can be tested with a type-I error rate of 2.5% and 99% power. An event rate of 32.5% was assumed for the active control and test group, which was then later adjusted to be 51% based on pooled analysis after 159 randomized patients. A sample size re-estimation was conducted after 159 randomized patients.

For the two co-primary tests, a sample size of approximately 350 was obtained by setting the non-inferiority margin at 19.1%, power at 94.5% and a 1-sided alpha at 0.025 assuming an event rate of 51%.

For the secondary endpoints involving ≥ 10 times troponin and comparing short tirofiban to eptifibatide, a sample size of approximately 500 was obtained by setting the noninferiority margin at 12.4%, power at 85% and a 1-sided alpha at 0.025 assuming an event rate of 32% (based on ≥ 10 times troponin elevation data from the 159 randomized patients).

SAS version 9.2 (SAS Institute, Cary, NC) was used for the sample-size calculations.

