2.9.1.3 Definition of Composite Endpoint

- Death due to any cause will be assessed through to 48 hours following PCI or hospital discharge, whichever comes first.
- Periprocedural myonecrosis will have occurred if there is at least one troponin (troponin I or troponin T) value of ≥ 3 times the upper limit of normal and at least 20% or greater than the baseline troponin value, per the troponin Local Laboratory, within 48 hours following PCI or hospital discharge, whichever comes first.
 - To be included in the primary composite endpoint analysis and in the secondary PPM endpoint analysis, a patient must have the pre-PCI troponin Local Laboratory measurement and at least one troponin Local Laboratory measurement within 48 hours following PCI or hospital discharge, whichever comes first.

- Patients without a pre-PCI troponin Local Laboratory measurement will not be included in the PPM endpoint analysis but will still be included in the intention to treat analysis and be analyzed for death and uTVR.
 - Patients without any troponin Local Laboratory measurements within 48 hours following PCI or hospital discharge, whichever comes first will not be included in the PPM endpoint analysis but will still be included in the intention to treat analysis and be analyzed for death, uTVR and major bleeding.
- Urgent Target Vessel Revascularization (uTVR) is either a PCI following the index PCI, or any CABG procedure performed after the index PCI on a non-selective basis in the target vessel because of recurrent myocardial ischemia. A revascularization procedure in the target vessel is considered urgent if it is due to one or more episodes of chest pain, presumed to be ischemic in origin and lasting at least 5 minutes, and results in either urgent repeat PCI or urgent coronary artery bypass surgery involving the target vessel. In the absence of pain, new ischemic ST-segment or T-wave changes, acute pulmonary edema, ventricular arrhythmias presumed to be ischemic in origin will constitute sufficient evidence of ischemia. The episode of ischemia leading to urgent repeat PCI must occur following completion of the index PCI and guidewire removal. For uTVR to count towards the primary composite endpoint, uTVR will have to be initiated during the course of the study (i.e., 48 hours following PCI or hospital discharge, whichever comes first).
- Major bleeding is defined using the criteria from the REPLACE-2 trial. Major bleeding is defined as follows:

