3.10 Analysis of the Study Endpoints

3.10.1 Analysis of the Primary Endpoint

To evaluate the effectiveness of tirofiban versus eptifibatide, we look at the proportion of patients with at least one of the following endpoint measurements: death, PPM, uTVR or REPLACE-2 Major bleeding within 48 hours following PCI or hospital discharge, whichever comes first. For each pairwise comparison:

- The short tirofiban group is non-inferior to the eptifibatide group;
- The short tirofiban group is non-inferior to the long tirofiban group;
- The long tirofiban group is non-inferior to the eptifibatide group;

The following hypothesis will be tested:

$$H_0: C - T \leq -0.191$$

$$H_1: C - T > -0.191$$

To test this hypothesis, the difference ($C - T$) and its associated one-sided 97.5% confidence interval will be calculated. If the lower bound of the interval is greater than -0.191, the non-inferiority will be claimed. In order to compute the risk (proportion) difference for data with binary

response (“Yes” vs. “No”), a bivariate logistic regression will be performed for each pairwise comparison with the following specifications:

- The dependent variable will be “composite endpoint” and the independent factor will be “treatment group”;
- The risk (proportion) difference between two methods as well as its confidence interval will be estimated;
- The non-inferiority margin is 19.1%

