3.10.4 Potential Covariates and/or Subgroups

As an exploratory analysis, appropriate univariate statistics will be used to identify potential confounders for inclusion in multivariable regression models for assessment of the primary endpoint. The following covariates will be considered:

- Patient with acute coronary syndromes (defined as any previous diagnosis of unstable angina, NSTEMI or STEMI)
- STEMI > 48 hours
- Stable angina
- Baseline troponin (positive vs. negative)
- Planned PCI access (femoral vs. radial)
- Number of stents implanted
- Number of vessels treated (multivessel vs. single vessel)
- Total infusion time
- Patients receiving P2Y12 antagonist therapy between 24 and 6 hours prior to randomization
- Patients receiving P2Y12 antagonist therapy between 6 and 1 hours prior to randomization
- Patients receiving P2Y12 antagonist therapy between 1 hour prior to randomization and 15 minutes after completion of the PCI procedure
- Type 2 diabetes mellitus
- Age < 65 years, ≥ 65-74 years and ≥ 75 years
- Sex
- Clopidogrel
- Prasugrel
- Ticagrelor
- Indication for PCI (Urgent vs. Elective)

RESPONSIVE
RELIABLE
RESULTS

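### The primary model adjusts for neither baseline troponin nor the access-site stratum: a modest, avoidable loss of precision, not a bias

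*SAP*

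**What the plan says.** SAP 3.10.1 compares each pair of arms by logistic regression of the composite on treatment group alone. From that model, "The risk (proportion) difference between two methods as well as its confidence interval will be estimated", and non-inferiority is claimed if the lower bound for control minus test exceeds -0.191.

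Three other provisions bear on this:

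- **Baseline troponin.** Pre-PCI sampling is mandated (Protocol Appendix 1; SAP Table 1). SAP 2.9.1.3 and Protocol 6.2 say that to enter the primary composite analysis "a patient must have the pre-PCI troponin Local Laboratory measurement", together with at least one post-PCI value. Periprocedural myonecrosis (PPM) is itself a troponin outcome: at least 3 times the upper limit of normal (ULN), plus a 20% condition against baseline.
- **Stratification.** Randomisation is stratified by femoral or radial access only (Protocol 5.2.2; SAP 2.8).
- **Adjustment elsewhere.** SAP 3.10.4 lists baseline troponin (positive or negative) and planned access among candidates for an exploratory multivariable model, chosen by univariate screening. Table 15(a) reports a risk difference from it. Protocol 9.6 promises to investigate important baseline imbalances and permits adjustment if judged necessary.

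**The concern.** A baseline measurement of the same biomarker that defines the main outcome component would normally be considered for the primary model. Here it costs nothing extra, since a patient without it is already excluded from the primary composite analysis. Factors used to stratify randomisation would normally be in the model too.

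PPM probably dominates the composite. SAP 2.6 gives 32% from the data on troponin elevations of at least 10 times ULN, and 51% for the pooled composite, both from the first 159 patients. If 32% is the rate of such elevations, PPM accounts for at least about 32/51 = 63% of composite events.

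The existing provisions do not supply a dependable adjusted estimate. The SAP 3.10.4 candidates include total infusion time, which is determined after randomisation and largely by arm (1–2 hours against 12–18 hours post-PCI). If selected, it could absorb the treatment contrast. Number of stents and number of vessels treated are also fixed after randomisation. The Protocol 9.6 clause is triggered by the data, in an open-label trial.

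At stake are the width of the interval compared with 19.1 points, and whether the adjusted estimate is fixed in advance.

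**Working it through.** **Inputs from the documents.** SAP 2.6: "the first primary outcome can be tested with a type-I error rate of 2.5% and 99% power"; the event rate was "adjusted to be 51% based on pooled analysis after 159 randomized patients". SAP 3.10.1: margin 19.1 points. Protocol synopsis: "A sample size of approximately 500 for the comparison between the short tirofiban and the eptifibatide group". SAP 2.6, for each co-primary test: "a sample size of approximately 350 was obtained by setting the non-inferiority margin at 19.1%, power at 94.5% and a 1-sided alpha at 0.025".

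**Step 1: reproduce the plan's sizes.** Unpooled variance, equal arms, true difference zero:

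n per arm = (z₀.₉₇₅ + z_power)² × 2p(1−p) / margin², with 2 × 0.51 × 0.49 = 0.4998 and 0.191² = 0.03648.

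- 99% power: (1.960 + 2.326)² × 0.4998 / 0.03648 = 251.7, so 252 per arm and 504 in total, against about 500.
- 94.5% power: (1.960 + 1.598)² × 0.4998 / 0.03648 = 173.5, so 174 per arm and 348 in total, against about 350.

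Both reproduce.

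**Step 2: precision as planned.** SE = √(0.4998/n); power = Φ(0.191/SE − 1.960).

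- 250 per arm: SE 0.04471, half-width 8.76 points, power Φ(4.272 − 1.960) = 98.96%.
- 175 per arm: SE 0.05344, half-width 10.47 points, power Φ(3.574 − 1.960) = 94.7%.

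**Step 3: effect of adjusting for baseline troponin.** Let q be the share baseline-positive and d the gap in composite risk between positive and negative patients. **Neither is in the documents; both are assumptions.** The variance is multiplied by 1 − R², where R² = q(1−q)d² / (0.51 × 0.49). Take q = 0.30, with d = 0.20 (65% vs 45%) or d = 0.40 (79% vs 39%):

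- d = 0.20: R² = 0.21 × 0.04 / 0.2499 = 0.034; SE ratio √0.966 = 0.983.
- d = 0.40: R² = 0.21 × 0.16 / 0.2499 = 0.134; SE ratio √0.866 = 0.930.

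| Comparison | Unadjusted | d = 0.20 | d = 0.40 |
|---|---|---|---|
| 250 per arm, half-width (points) | 8.76 | 8.61 | 8.15 |
| 250 per arm, power | 98.96% | 99.15% | 99.6% |
| 175 per arm, half-width (points) | 10.47 | 10.30 | 9.74 |
| 175 per arm, power | 94.7% | 95.3% | 97.0% |

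Across q = 0.2 to 0.5 and d = 0.1 to 0.5, the half-width falls by 0.3% to 13%. Power is then 99.0% to 99.85% at 500 patients and 94.8% to 98.5% at 350.

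**Step 4: size of chance imbalance.** The SD of its effect on the crude difference is d√(2q(1−q)/n). For q = 0.30 this is 0.8 to 1.6 points at 250 per arm and 1.0 to 2.0 points at 175 per arm. This is the same variance that Step 3 removes, not an additional error.

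**Step 5: simulation.** Crude and troponin-standardised risk differences were compared over 20,000 trials per scenario (q = 0.3 with d = 0.2 or 0.4; q = 0.5 with d = 0.3). With no true difference, the two decisions disagreed in 0.4% to 0.8% of trials at 500 patients and 1.5% to 2.8% at 350. With the true difference at the margin, the crude test's type I error was 2.3% to 2.6%, against a nominal 2.5%.

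The documents give nothing from which to size the gain from planned access.

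**The case against.** The strongest case against is that nothing here is an error. A crude risk difference in a randomised trial is valid and holds its type I error. A reader might infer that a chance excess of troponin-positive patients biases the non-inferiority decision. The documents do not support that: such imbalance is random error, already inside the confidence interval. This objection stands in full.

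A reader might also take baseline troponin to be a known strong predictor. The documents do not show this either. The 3-times-ULN condition makes patients with a raised baseline more likely to qualify, while the 20% condition can make them less likely, for instance when a high baseline is falling. The relation may be weak or non-monotone. The gain depends on d², so the sign of the gap does not matter, but its size is unknown. This stands, and is why only a range is given.

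It may also be said that the plan already adjusts. That stands in part: Table 15(a) is a real adjusted analysis and Protocol 9.6 a real provision. But the first is exploratory and screened, the second is discretionary, and neither governs the decision.

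Finally, the mITT definition in SAP 3.2 carries no troponin condition and Table 14 is headed mITT, so a troponin-adjusted model might appear to drop patients. SAP 2.9.1.3 and Protocol 6.2 already exclude those without a baseline value from the primary composite analysis. They remain only for other analyses such as death and urgent revascularisation. None is lost, but SAP 3.10.1 should say so.

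**Conclusion.** The point holds as lost precision, not bias. SAP 3.10.1 omits the stratification factor and a baseline value that the primary composite analysis already requires, and no other provision supplies a pre-specified adjusted estimate.

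The likely gain is modest. With 30% baseline-positive and a 20- to 40-point risk gap, both assumed, the interval narrows by about 1.7% to 7%. That is worth 0.2 to 0.6 power points on the first primary test and 0.6 to 2.3 points on each co-primary test. On a first test planned at 99% power, the conclusion would rarely change.

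The co-primary figures assume 175 per arm, and the plan does not state arm sizes. Pairwise totals of 500, 350 and 350 would instead imply arms of 250, 250 and 100, or 600 in all rather than about 550. At 250 against 100, power is 89.8% unadjusted and 90.7% to 93.5% adjusted on the same assumptions. Arm size therefore matters more to those tests than the missing covariate.

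**What to change.** Before by-arm outcomes are examined, amend SAP 3.10.1 as follows:

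1. Make the primary estimate a risk difference standardised from a logistic model with treatment, planned access and baseline troponin. Average each patient's predicted risk under each arm over the analysed patients, and state how the confidence interval is computed. The estimate then stays on the scale of the margin.
2. State one coding of baseline troponin. One option is the log of the multiple of the local laboratory's ULN, because troponin I and T from local laboratories are mixed, with a flexible term or categories to allow a non-monotone relation. If positive/negative is used instead, define the cut-off, which the plan does not give.
3. Exclude total infusion time and other post-randomisation variables, such as number of stents and vessels treated, from this model and from the adjusted models of Table 15(a).
4. Keep the -0.191 rule and report the unadjusted estimate as supportive.
5. State that patients without a pre-PCI troponin are already outside the primary composite analysis under SAP 2.9.1.3, and reconcile this with the mITT definition in SAP 3.2.

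SAP 3.10.2 analyses the secondary endpoints in the same way, so state whether the adjusted method applies there. The cost is SAP wording and a standard post-estimation step. No new data are needed and no patients are lost.

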3.10.2 Analysis of the Secondary Endpoints

The analysis of the secondary endpoints will be conducted in the same way as for the primary endpoint.

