1.4.2 Clinical Studies Conducted with Tirofiban High-Dose Bolus Regimen

Based on the published findings demonstrating that a higher bolus dose of tirofiban provided platelet inhibition on par with abciximab during the PCI peri-procedural period, the TENACITY trial was initiated by Guilford Pharmaceuticals. Unfortunately, due to financial constraints, TENACITY was halted in June 2005, after enrolling 383 patients out of a planned 8000.

TENACITY was a double-blind, randomized active-comparator study comparing the high-dose bolus regimen of tirofiban to abciximab in intermediate to high-risk ACS patients. A second randomization assigned patients to receive either unfractionated heparin or bivalirudin as their direct thrombin inhibitor. All patients received clopidogrel and aspirin prior to randomization.

The results of the TENACITY study were analyzed with the 383 patients enrolled in the study and recently published [62]. At 30-days there was a non-significant difference between high-dose bolus tirofiban and abciximab, and the percent of patients with death, non fatal MI or urgent target vessel revascularization was 6.9% in the high-dose bolus tirofiban group versus 8.8% in the abciximab group (P=NS). This difference was driven primarily by an almost 2% absolute difference in rates of non-fatal myocardial infarction between high-dose bolus tirofiban and abciximab (5.9% vs. 7.7%; P=NS). There were no differences in bleeding between the two groups. When analyzed for combined death, MI, urgent TVR and major bleeding at 30-days, the combination of high-dose bolus tirofiban

and bivalirudin (5.6%) was non-significantly lower than abciximab and UFH (9.1%), abciximab and bivalirudin (10.5%), and high-dose bolus tirofiban and UFH (10.1%).

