9.2 Statistical Alternative Hypothesis (Ha)

The first primary test is that short tirofiban is non-inferior to eptifibatide for death, PPM, uTVR or REPLACE-2 Major bleeding within 48 hours following PCI or hospital discharge, whichever comes first. The original non-inferiority margin was 12.4% (with an expected pooled rate of 32.5%), but based on the higher observed pooled event rate of 51% after 159 randomized patients, the non-inferiority margin was revised to be 19.1% in order to maintain the same relative margin (i.e. $12.4\% / 32.5\% = 19.1\% / 51\% = 0.38$) For the co-primary tests, the same non-inferiority margin (19.1%) will be used.

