9.3.2 Secondary Endpoint and Associated Tests

First secondary test: A short tirofiban regimen of a high-dose bolus plus a shortened infusion duration is non-inferior to label-dosing eptifibatide among patients undergoing PCI with respect to the following list:

- death, PPM or uTVR within 48 hours following PCI or hospital discharge, whichever comes first
- PPM within 48 hours following PCI or hospital discharge, whichever comes first
- uTVR within 48 hours following PCI or hospital discharge, whichever comes first
- death within 48 hours following PCI or hospital discharge, whichever comes first
- death, PPM, uTVR or major bleeding within 48 hours following PCI or hospital discharge, whichever comes first, where PPM is defined as at least one troponin elevation of ≥ 10 times the upper limit of normal AND at least 20% of greater than the baseline troponin value, per the troponin Local Laboratory within 48 hours following PCI or hospital discharge, whichever comes first (a non-inferiority margin of 12.4% will be used for the short tirofiban versus eptifibatide comparison)
- at least one troponin elevation of ≥ 10 times the upper limit of normal AND at least 20% of greater than the baseline troponin value, per the troponin Local Laboratory, within 48 hours following PCI or hospital discharge, whichever comes first (a non-inferiority margin of 12.4% will be used for the short tirofiban versus eptifibatide comparison)
- at least one troponin elevation of ≥ 20 times the upper limit of normal AND at least 20% of greater than the baseline troponin value, per the troponin Local Laboratory, within 48 hours following PCI or hospital discharge, whichever comes first

- at least one troponin elevation of ≥ 50 times the upper limit of normal AND at least 20% of greater than the baseline troponin value, per the troponin Local Laboratory, within 48 hours following PCI or hospital discharge, whichever comes first.
- Co-secondary tests: (i) a short tirofiban regimen of a high-dose bolus plus a 1-2 hour infusion duration post procedure is non-inferior to a long tirofiban regimen of a high-dose bolus plus a 12-18 hour infusion, and (ii) a long tirofiban regimen of a high-dose bolus plus a 12-18 hour infusion is non-inferior to label-dosing eptifibatide with respect to the same secondary tests in the list above.

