9.5 Sample Size Calculations

The primary outcome variable for this trial is the composite of death, PPM, uTVR or REPLACE-2 Major bleeding.

Sample size calculations ensure that the one-sided non-inferiority hypothesis of the first primary outcome can be tested with a type-I error rate of 2.5% and 99% power. An event rate of 32.5% will be assumed for the active control and test group which was then later assumed to be 51% based on pooled analysis after 159 randomized patients. A sample size re-estimation was conducted after 159 randomized patients.

For the two co-primary tests, a sample size of approximately 350 was obtained by setting the non-inferiority margin at 19.1%, power at 94.5% and a 1-sided alpha at 0.025 assuming an event rate of 51%.

For the secondary endpoints involving ≥10 times troponin and comparing short tirofiban to eptifibatide, a sample size of approximately 500 was obtained by setting the non-inferiority margin at 12.4%, power at 85% and a 1-sided alpha at 0.025 assuming an event rate of 32% (based on ≥10 times troponin elevation data from the 159 randomized patients).

SAS version 9.2 (SAS Institute, Cary, NC) was used for the sample-size calculations.

The trial may be terminated for futility at an interim point in time. Details of the methodology and stopping boundaries will be provided in the Statistical Analysis Plan.

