9.6 Planned Methods of Analysis

General Principles

For continuous variables, descriptive statistics (mean, SD, median, and quartiles) will be tabulated by treatment group. For categorical variables, the number and proportion of patients in each category will be tabulated.

The primary and secondary endpoints will be analyzed using the MITT population. Safety endpoints will be analyzed using the safety population. Demographics, baseline characteristics, and other study assessments will be analyzed using the MITT and intent-to-treat (ITT) population.

Confidence intervals will be used to assess hypotheses of non-inferiority and superiority. Details of the statistical methods will be developed in the Statistical Analysis Plan (SAP).

Demography and Baseline Characteristics

All appropriate background data will be summarized for each treatment group. If there are heterogeneities between two groups in any of the patient characteristics that are of clinical importance or could affect the study outcome, the impact of the imbalances will be investigated. If necessary, adjustments may be made in the efficacy and safety analysis and will be documented in the study report.

Primary Endpoint

The first primary and co-primary endpoints will be analyzed by the use of a one-sided 97.5% confidence interval

Subgroup/Covariate Analyses

Formal subgroup analyses will be performed by including the appropriate interaction terms in multivariable logistic regression models. The effects of potential covariates (see Section 9.3.4) will be assessed using multi-variable logistic regression.

Secondary Endpoints

The analysis of the secondary endpoints will be conducted in the same way as for the primary endpoint.

Safety Endpoints

The analysis of these safety endpoints will compare the incidence in the short tirofiban treatment group to the incidence in the eptifibatide group, the incidence in the short tirofiban treatment group to the incidence in the long tirofiban treatment group and the incidence in the long tirofiban treatment group to the incidence in the eptifibatide group, using the Fisher's mid-p (Berry and Armitage, 1995). Serious adverse events will also be tabulated overall and by severity for each treatment group.

Multiplicity (Multiple Endpoints)

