2.9.1.2 Secondary Endpoints

Secondary endpoints will be:

- First secondary test: A short tirofiban regimen of a high-dose bolus plus a shortened infusion duration is non-inferior to label-dosing eptifibatide among patients undergoing PCI with respect to the following list:
 - death, PPM or uTVR within 48 hours following PCI or hospital discharge, whichever comes first
 - PPM within 48 hours following PCI or hospital discharge, whichever comes first
 - uTVR within 48 hours following PCI or hospital discharge, whichever comes first
 - death within 48 hours following PCI or hospital discharge, whichever comes first
 - death, PPM, uTVR or major bleeding within 48 hours following PCI or hospital discharge, whichever comes first, where PPM is defined as at least one troponin elevation of ≥ 10 times the upper limit of normal and at least 20% of greater than the baseline troponin value, per the troponin Local Laboratory within 48 hours following PCI or hospital discharge, whichever comes first (a non-inferiority margin of 12.4% will be used for the short tirofiban versus eptifibatide comparison)
 - at least one troponin elevation of ≥ 10 times the upper limit of normal and at least 20% of greater than the baseline troponin value, per the troponin Local Laboratory, within 48 hours following PCI or hospital discharge, whichever comes first (a

noninferiority margin of 12.4% will be used for the short tirofiban versus eptifibatide comparison)

- at least one troponin elevation of ≥ 20 times the upper limit of normal and at least 20% of greater than the baseline troponin value, per the troponin Local Laboratory, within 48 hours following PCI or hospital discharge, whichever comes first
 - at least one troponin elevation of ≥ 50 times the upper limit of normal and at least 20% of greater than the baseline troponin value, per the troponin Local Laboratory, within 48 hours following PCI or hospital discharge, whichever comes first.
- Co-secondary tests:
- (i) a short tirofiban regimen of a high-dose bolus plus a 1-2 hour infusion duration post procedure is non-inferior to a long tirofiban regimen of a high-dose bolus plus a 12-18 hour infusion, and
 - (ii) a long tirofiban regimen of a high-dose bolus plus a 12-18 hour infusion is non-inferior to label-dosing eptifibatide with respect to the same secondary tests in the list above.

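### Most secondary non-inferiority tests, including death alone and uTVR alone, have no margin of their own, and the primary's 19.1 points does not fit 16 of them

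*SAP*

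**What the plan says.** Protocol 9.3.2 and SAP 2.9.1.2 list eight secondary endpoints, each worded as a statement that one regimen is non-inferior to another. One entry is "death within 48 hours following PCI or hospital discharge, whichever comes first"; uTVR alone is another. The same list applies to all three comparisons: short tirofiban versus eptifibatide, short versus long tirofiban, and long tirofiban versus eptifibatide.

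A margin appears only beside the two endpoints that use troponin at least 10 times ULN, where "a non-inferiority margin of 12.4% will be used for the short tirofiban versus eptifibatide comparison".

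For the method, Protocol 9.6 states that "Confidence intervals will be used to assess hypotheses of non-inferiority and superiority" and leaves the details to the SAP. SAP 3.10.2 consists of one sentence: "The analysis of the secondary endpoints will be conducted in the same way as for the primary endpoint". The primary rule, in SAP 3.10.1, takes the control rate minus the test rate (C − T) with a one-sided 97.5% interval: "If the lower bound of the interval is greater than -0.191, the non-inferiority will be claimed".

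Protocol 9.2 explains where 19.1 came from. After a pooled event rate of 51% was seen in the first 159 patients, "the non-inferiority margin was revised to be 19.1% in order to maintain the same relative margin", a ratio of about 0.38. That section extends the margin by name to the co-primary tests and to nothing else.

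**The concern.** An absolute margin has meaning only against the event rate it was set for. The 19.1-point margin was built for a composite expected in about half of the patients. Applied to a rare component such as death, it allows an excess many times larger than the rate itself, so a non-inferior result says almost nothing. If the margin does not carry over, the plan declares tests that have no criterion, and one would have to be chosen at the analysis stage.

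At stake is a written statement that a tirofiban regimen is non-inferior on death or uTVR when the data could show the opposite. The primary result is not affected.

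**Working it through.** **1. The plan's own sizes reproduce.** Per-arm n = (z₀.₉₇₅ + z_power)² × 2p(1 − p) / margin².
- First primary test (51%, 19.1 points, 99% power): (1.960 + 2.326)² × 0.4998 / 0.03648 gives 252 per arm, 504 in total. The plan says about 500.
- Co-primary tests (51%, 19.1 points, 94.5% power): 174 per arm, 348 in total. The plan says about 350.
- At least 10 times ULN, "power at 85% and a 1-sided alpha at 0.025 assuming an event rate of 32" per cent, 12.4 points: 255 per arm, 510 in total. The plan says about 500.

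So the margins are absolute percentage points, used as read here. An arm size of 250 is assumed from about 500 patients allocated 1:1 between these two arms in every phase.

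**2. Count of tests.** 8 endpoints × 3 comparisons = 24. Two have 12.4 points; 22 have no stated margin.

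**3. What the 19.1-point rule would accept for death.** A lower bound of C − T above −19.1 is the same as an upper bound of T − C below 19.1. Take 36/250 (14.4%) versus 1/250 (0.4%), a difference of 14.0 points.
- Wald: SE = √(0.144 × 0.856/250 + 0.004 × 0.996/250) = 0.02256. The upper bound is 14.0 + 1.96 × 2.256 = 18.4 points. The treatment-only logistic model with the delta method gives the same bound.
- Newcombe: the Wilson upper limit for 36/250 is 19.29% and the Wilson lower limit for 1/250 is 0.07%. The upper bound is 14.0 + √(4.89² + 0.33²) = 18.9 points.
- Both are below 19.1, so the rule is met. At 37 versus 1 the Wald bound (18.87) passes and the Newcombe bound (19.34) fails.

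If the true death rates were 10% and 1% (illustrative, 250 per arm), summing the exact binomial probabilities over all outcomes that pass gives 99.6% (Wald) or 99.3% (Newcombe).

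The long-tirofiban arm size is not stated. Assuming 175/175 (an even split of 350), 23 versus 1 passes (17.7 Wald, 18.4 Newcombe). Assuming 100 long versus 250 eptifibatide, 11 versus 1 passes (16.8, 18.2).

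**4. Where 19.1 points does not fit.** The plan's own ratios are 0.124/0.325 = 0.38, 0.191/0.51 = 0.37 and, for at least 10 times ULN, 0.124/0.32 = 0.39.
- *Death alone, uTVR alone (2 × 3 = 6 tests).* The documents give no rate for this trial. Protocol 1.4.2 cites a 383-patient trial in which 30-day death, non-fatal MI or uTVR together was "6.9% in the high-dose bolus tirofiban group versus 8.8% in the abciximab group". Neither death alone nor uTVR alone could exceed 8.8% there, so 19.1 is at least 19.1/8.8 = 2.2 times that rate.
- *At least 10 times ULN, two endpoints in the two long-tirofiban comparisons (2 × 2 = 4 tests).* 0.191/0.32 = 0.60. For example, 39/100 versus 80/250 passes at 19.1 points (18.2 by Wald and Newcombe); at 12.4 points the most that passes is 33/100.
- *At least 20 times and at least 50 times ULN (2 × 3 = 6 tests).* Both carry the same 20%-over-baseline condition and are subsets of at least 10 times ULN. On the plan's 32% they cannot exceed 32%, so 19.1 is at least 0.60 of their rate.

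Total: 6 + 4 + 6 = 16. The remaining 22 − 16 = 6 tests are PPM alone and death, PPM or uTVR.

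**5. Empty arms.** The treatment-only logistic model has no finite treatment estimate if an arm has no events. At assumed rates of 0.5% and 1%, the chance that at least one of two arms of 250 is empty is 1 − (1 − 0.995²⁵⁰)² = 49% and 1 − (1 − 0.99²⁵⁰)² = 16%.

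**The case against.** The strongest reply is that the plan never says 19.1 points applies to death. Protocol 9.2 names only the primary and co-primary tests, SAP 3.10.1 attaches the margin to a model of the composite endpoint, and SAP 3.10.2 may mean the method alone. This stands in part: the carry-over is a reading, not a stated rule. But SAP 3.10.1 lists the margin among the specifications of the analysis to be repeated, so carry-over is the literal reading. The other reading leaves non-inferiority tests with no margin. Both need repair.

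Second, the consequence is small. Nothing in the documents suggests 14.4% mortality within 48 hours or discharge. SAP 3.11 ties any claim of effect to the primary endpoint. Mock Tables 14 and 16 show the counts, and Table 17 prints the odds ratio, risk difference and intervals with no verdict column. For 36 versus 1 it would show an odds ratio of 41.9 (95% CI 5.7 to 308), p = 0.0002. All of this stands. The 36 versus 1 case is not a forecast; it shows what the rule cannot detect. SAP 3.11 does not withdraw the secondary tests or set their margins.

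A reader might also go further and subtract MI from the cited composite (6.9 − 5.9 and 8.8 − 7.7, about 1 point) to argue that 19.1 is some 19 times the rate of death or of uTVR. The documents do not support that. The remainder is for death or uTVR jointly, at 30 days, in another trial, and either alone could be zero. Only the 8.8% ceiling can be used.

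**Conclusion.** The concern holds. Of 24 secondary non-inferiority tests, 22 have no margin of their own. If the primary's 19.1 points carries over, it is out of proportion to the endpoint in 16 of them, and on death it would pass 36 versus 1 at 250 per arm. If it does not carry over, all 22 lack a criterion.

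The size rests on the assumed 250 per arm, on the cited trial's 8.8% as a ceiling for death or uTVR, and on the plan's 32% for at least 10 times ULN.

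Two stronger inferences fail. The documents do not show that 19.1 is wrong for PPM alone or for death, PPM or uTVR: no planning rate is given for these 6 tests, and they only lack a stated margin. Nor is the trial's main claim at risk. The harm is confined to secondary conclusions, but the point should be fixed before the final analysis, since choosing a margin or a reading afterwards would be data-driven.

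**What to change.** In SAP 3.10.2 before the final analysis, and in Protocol 9.3.2 and 9.6 at the next amendment:

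1. State that the 19.1-point margin does not apply to the secondary endpoints.
2. **Death alone and uTVR alone:** report counts and the risk difference with a score or exact interval, which also handles an empty arm, and draw no non-inferiority conclusion. A scaled margin would not rescue these tests. Even at 8.8%, 0.38 × 8.8 = 3.3 points gives only about 26% power at 250 per arm, and less at lower rates.
3. **At least 10 times ULN, short tirofiban versus eptifibatide:** keep 12.4 points.
4. **All other secondary tests:** report the interval without a non-inferiority conclusion, or fix a margin beforehand from the 0.38 ratio and a pre-stated rate, not from the final trial data.

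Cost: SAP wording and a change of interval method, since Table 17 already prints risk differences with 95% intervals. The protocol change needs IRB approval under Protocol 19. The sponsor gives up some secondary non-inferiority claims that carry little evidence. If 12.4 points were chosen for the long-tirofiban comparisons at 32%, power would be about 70% (175/175), 61% (100/250) or 40% (50/250), depending on the unstated arm size, against the planned 85% for short tirofiban versus eptifibatide.
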